### 3.3 Eligibility Criteria

Patients must have baseline evaluations performed prior to the first dose of study drug and must meet all inclusion and exclusion criteria. In addition, the patient must be thoroughly informed about all aspects of the study, including the study visit schedule and required evaluations and all regulatory requirements for informed consent. The written informed consent must be obtained from the patient prior to enrollment. The following criteria apply to all patients enrolled in the study unless otherwise specified.

#### 3.3.1 Inclusion Criteria

1. Pre and postmenopausal women or men with stage IV ER+ breast cancer histological or cytological confirmation, 18 years of age or older.

Because no dosing or adverse event data are currently available on the use of pembrolizumab, vorinostat, or tamoxifen in patients <18 years of age, children are excluded from this study but will be eligible for future pediatric trials.

2. >10% expression of PD-1/CTLA-4 dual staining in CD8 cells in tumor or blood or  $\geq 5\%$  expression of PD-1/CTLA-4 dual staining in CD4 in blood (only).
3. Eastern Cooperative Oncology Group (ECOG) Performance Status of  $\leq 1$ .
4. Understand and voluntarily sign an informed consent prior to any study-related assessments or procedures are conducted and are able to adhere to the study visit schedule and other protocol requirements.
5. Consent to paired tumor biopsy
6. Measurable tumor by RECIST criteria
7. Per Good Clinical Practice, any toxicity related to prior therapies that, in the opinion of the investigator, would potentially be worsened with anti-PD1 therapy should be resolved to less than Grade 1
8. Adequate organ function:
  - Absolute neutrophil count (ANC)  $\geq 1.5 \times 10^9/L$
  - Hemoglobin (Hgb)  $\geq 9g/dL$  (may transfuse if clinically indicated)
  - Platelets (plt)  $\geq 100 \times 10^9/L$
  - Potassium within normal range, or correctable with supplements;
  - AST and ALT  $\leq 2.5 \times$  Upper Limit Normal (ULN) or  $\leq 5.0 \times$  ULN if liver tumor is present;
  - Serum total bilirubin  $\leq 1.5 \times$  ULN
  - Serum creatinine  $\leq 1.5 \times$  ULN, or 24-hr clearance  $\geq 60ml/min$ ; and
9. Females of childbearing potential (defined as sexually mature women who):
  - Has not undergone a hysterectomy (the surgical removal of the uterus) or bilateral oophorectomy (the surgical removal of both ovaries) or,
  - Has not been naturally postmenopausal for at least 24 consecutive months (i.e., has had menses at any time during the preceding 24 consecutive months) must have
    - Negative serum pregnancy test within 14 days before starting study treatment in females of childbearing potential (FCBP) and willingness to adhere to acceptable forms of birth control (a physician-approved contraceptive method (oral, injectable, or implantable hormonal contraceptive; tubal ligation; intra-uterine device; barrier contraceptive with spermicide; or vasectomized partner)
10. All female and male participants must agree to use approved contraception during the treatment period and for at least 18 weeks after the last dose of study treatment and refrain from donating sperm during this period.

### 3.3.2 Exclusion Criteria

1. Prior treatment with pembrolizumab or other PD-(L)1
2. Any significant medical condition, laboratory abnormalities, which places the subject at unacceptable risk if he/she were to participate in the study.
3. Has a history of (non-infectious) pneumonitis/interstitial lung disease that required steroids or current pneumonitis/ interstitial lung disease.
4. Has known active Hepatitis B (e.g., HBsAg reactive) or Hepatitis C (e.g., HCV RNA [qualitative] is detected)"
5. Has a history of HBV
6. Has a history or current evidence of any condition, therapy, or laboratory abnormality that might confound the results of the study, interfere with the subject's participation for the full duration of the study, or is not in the best interest of the subject to participate, in the opinion of the treating investigator
7. Symptomatic central nervous system metastases. Subjects with brain metastases that have been previously treated and are stable for 6 weeks are allowed.
8. Persistent diarrhea or malabsorption  $\geq$  NCI CTCAE grade 2, despite medical management.
9. Unstable angina, significant cardiac arrhythmia, or New York Heart Association (NYHA) class 3 or 4 congestive heart failure.
10. Prior systemic cancer-directed treatments or investigational modalities  $\leq$  5 half-lives or 4 weeks, whichever is shorter, prior to starting study drug or who have not recovered from side effects of such therapy (except alopecia).
11. Active autoimmune disease except for vitiligo or hypothyroidism
12. Active and ongoing steroid use, except for non-systemically absorbed treatments (such as inhaled or topical steroid therapy for asthma, COPD, allergic rhinitis).
13. Major surgery  $\leq$  2 weeks prior to starting a study drug or who have not recovered from side effects of such therapy.
14. Pregnant or breastfeeding.
15. Known Human Immunodeficiency Virus (HIV) infection
16. Known history of tuberculosis
17. Known allergic reaction or intolerability to tamoxifen
18. Patients with prior history of DVTs must be on therapeutic or preventive anticoagulation

### 3.4 Inclusion and Recruitment of Women and Minorities

Individuals of any sex/gender, race, or ethnicity may participate.

The study recruitment strategy aims to achieve representation of minority groups that reflects the demographics of the affected population in the catchment area.

### **3.5 Duration of Treatment**

Eligible patients will receive treatment as described above, in consecutive 3-week cycles, until progression of disease or unacceptable toxicity. Patients are expected to receive treatment for at least 3 cycles, at which time the first evaluation for efficacy will occur. If there is continued safety and tolerability, treatment may continue.

All patients will be restaged during at 9 weeks ( $\pm 1$  week) and 18 weeks ( $\pm 1$  week) via imaging scans; staging will then be continued every 3 cycles until 6 months. After 6 months, staging may be spaced out to 6 cycles if clinically indicated.

Patients will be followed for evaluation of safety for at least 30 days after the last dose of study drug. Any study drug-related serious adverse events will be followed until resolution, return to baseline grade, or deemed irreversible by the Investigator.

Subjects who experience a recurrence of the same severe or life-threatening event at the same grade or greater with re-challenge of pembrolizumab should be discontinued from trial treatment.

### **3.6 Duration of Follow Up**

Patients will be followed for 30 days after end of study participation or removal from study. Patients removed from study for unacceptable treatment-related adverse event(s) will be followed until resolution or stabilization of all treatment-related adverse events to Grade 2 or lower.

Subjects who discontinue for reasons other than progressive disease will have post-treatment follow-up for disease status until disease progression, initiating a non-study cancer treatment, withdrawing consent, or becoming lost to follow-up. After documented disease progression, each subject will be followed by telephone for overall survival until death, withdrawal of consent, or the end of the study, whichever occurs first.

Subjects may withdraw consent at any time for any reason or be dropped from the trial at the discretion of the investigator should any untoward effect occur. In addition, a subject may be withdrawn by the investigator or the Sponsor if enrollment into the trial is inappropriate, the trial plan is violated, or for administrative and/or other safety reasons. Specific details regarding discontinuation or withdrawal are provided in Section 5.4.

### **3.7 Randomization Procedures**

This is an open-label randomized trial; therefore, the sponsor, investigator, and subject will know the treatment administered. Two arms will be tested, with each independent assessment. Patients will be randomized to either arm using a computerized randomization program by [name]. Patients will be further stratified by prior number of chemo- and hormonal therapies.

### **3.8 Primary Completion**

The estimated primary completion is 36 months after the study opens to accrual.

### 3.9 Study Completion

The expected study completion date is 48 months after the study opens to accrual.

The study will conclude when all enrolled patients have been followed for more than 30 days following completion of the study. The estimated duration of study, from start of enrollment to final study report is 4 years.

## 4 Investigational Products

### 4.1 Description, Supply, and Storage of Investigational Products

#### 4.1.1 Investigational Product: Pembrolizumab (MK-3475)

##### Classification

Antineoplastic, Monoclonal antibody (mAb)

##### Mechanism of Action

Pembrolizumab (previously known as SCH 900475) is a potent and highly selective humanized monoclonal antibody (mAb) of the IgG4/kappa isotype designed to directly block the interaction between PD-1 and its ligands, PD-L1 and PD-L2. This blockade enhances functional activity of the target lymphocytes to facilitate tumor regression and ultimately immune rejection.

##### Metabolism

Pembrolizumab is catalyzed into small peptides and single amino acids via general protein degradation, but it does not rely on metabolism for clearance.

##### Contraindications

None

##### Formulation, Appearance, Packaging, and Labeling

Pembrolizumab is supplied as 100 mg/4 mL solution in a single-use vial for intravenous administration. Pembrolizumab is manufactured by Merck. Supplies will be labeled in accordance with regulatory requirements. This trial is open-label; therefore, the participant, the trial site personnel, the Sponsor, and/or designee are not blinded to treatment. Drug identity (name, strength) is included in the label text; random code/disclosure envelopes or lists are not provided.

##### Availability

Pembrolizumab is being obtained as commercial supply provided by Merck.

##### Storage and handling

Pembrolizumab is stored at the UCSF investigational pharmacy. Clinical supplies must be stored in a secure, limited-access location under the storage conditions specified on the label. Receipt and dispensing of trial medication must be recorded by an authorized person at the trial site. Clinical supplies may not be used for any purpose other than that stated in the protocol.

Store the diluted solution from the KEYTRUDA 100 mg/4 mL vial either:

- At room temperature for no more than 6 hours from the time of dilution. This includes room temperature storage of the diluted solution and the duration of infusion.

- Under refrigeration at 2°C to 8°C (36°F to 46°F) for no more than 24 hours from the time of dilution. If refrigerated, allow the diluted solution to come to room temperature prior to administration.

Discard after 6 hours at room temperature or after 24 hours under refrigeration.

Do not freeze.

#### Side Effects

Complete and updated adverse event information is available in the Investigational Drug Brochure (IB) and/or product package insert.

#### Returns and Reconciliation

The investigator is responsible for keeping accurate records of the clinical supplies received from Merck or designee, the amount dispensed to and returned by the participants and the amount remaining at the conclusion of the trial.

Upon completion or termination of the study, all unused and/or partially used investigational product will be destroyed at the site per institutional policy. It is the Investigator's responsibility to arrange for disposal of all empty containers, provided that procedures for proper disposal have been established according to applicable federal, state, local and institutional guidelines and procedures, and provided that appropriate records of disposal are kept.

### **4.1.2 Investigational Product: Vorinostat**

#### Classification

Antineoplastic

#### Mechanism of Action

Vorinostat, a histone deacetylase (HDAC) inhibitor. Histone deacetylases (HDACs) are a family of enzymes that regulate chromatin remodeling and gene transcription via the dynamic process of acetylation and deacetylation of core histones.

Vorinostat, a potent inhibitor of HDAC activity, binds directly to the catalytic pocket of HDAC enzymes. It causes G1 or G2 phase cell-cycle arrest, apoptosis, or differentiation in cultured transformed cells.

#### Metabolism

The major pathways of vorinostat metabolism involve glucuronidation and hydrolysis, followed by  $\beta$ -oxidation. Human serum levels of two metabolites, O-glucuronide of vorinostat and 4-anilino-4-oxobutanoic acid were measured. Both metabolites are pharmacologically inactive. Compared to vorinostat, the mean steady-state serum exposures in humans of the O-glucuronide of vorinostat and 4-anilino-4-oxobutanoic acid were 4-fold and 13-fold higher, respectively. In vitro studies using human liver microsomes indicate negligible biotransformation by cytochromes P450 (CYP).

#### Contraindications

None

#### Formulation, Appearance, Packaging, and Labeling

Vorinostat is supplied as size 3 100 mg capsules for oral administration. Vorinostat will be supplied in a 100-120 capsule bottle. Vorinostat will be given at 400 mg per day (4x 100 mg tablets), 4 of 7 days. Vorinostat is manufactured by Merck & Co., Inc.

#### Availability

Vorinostat is being obtained as commercial supply provided by Merck & Co., Inc.

#### Storage and handling

Vorinostat is stored at the UCSF investigational pharmacy. Store vorinostat capsules at room temperature, 15 to 30 .C (59 to 86 .F). Do not store above 30.C. Avoid exposure to excessive moisture.

Vorinostat is an anticancer drug. If clean powder is spilled from broken or damaged vorinostat capsules care should be taken to minimize inhalation or direct contact with skin. Wash spill area at least 3 times with ethyl alcohol, followed by water.

#### Side Effects

Complete and updated adverse event information is available in the current IB and/or product package insert.

### **4.1.3 Investigational Product: Tamoxifen**

#### Classification

Non-steroidal anti-estrogen

#### Mechanism of Action

Following a single oral dose of 20 mg tamoxifen, an average peak plasma concentration of 40 ng/mL (range 35 to 45 ng/mL) occurred approximately 5 hours after dosing. The decline in plasma concentrations of tamoxifen is biphasic with a terminal elimination half-life of about 5 to 7 days. The average peak plasma concentration of N-desmethyl tamoxifen is 15 ng/mL (range 10 to 20 ng/mL). Chronic administration of 10 mg tamoxifen given twice daily for 3 months to patients results in average steady-state plasma concentrations of 120 ng/mL (range 67-183 ng/mL) for tamoxifen and 336 ng/mL (range 148-654 ng/mL) for N-desmethyl tamoxifen. The average steady-state plasma concentrations of tamoxifen and N-desmethyl tamoxifen after administration of 20 mg tamoxifen once daily for 3 months are 122 ng/mL (range 71-183 ng/mL) and 353ng/mL (range 152-706 ng/mL), respectively.

After initiation of therapy, steady-state concentrations for tamoxifen are achieved in about 4 weeks, and steady-state concentrations for N-desmethyl tamoxifen are achieved in about 8 weeks, suggesting a half-life of approximately 14 days for this metabolite. In a steady state, crossover study of 10 mg NOLVADEX tablets given twice a day vs. a 20 mg NOLVADEX tablet given once daily, the 20 mg NOLVADEX tablet was bioequivalent to the 10 mg NOLVADEX tablets.

#### Metabolism

Tamoxifen is extensively metabolized after oral administration. N-desmethyl tamoxifen is the major metabolite found in patients' plasma. The biological activity of N-desmethyl tamoxifen appears to be similar to that of tamoxifen. 4-Hydroxytamoxifen and a side chain primary alcohol derivative of tamoxifen have been identified as minor metabolites in plasma. Tamoxifen is a substrate of cytochrome P-450 3A, 2C9 and 2D6, and an inhibitor of P-glycoprotein.

#### Excretion:

Studies in women receiving 20 mg of C tamoxifen have shown that approximately 65% of the administered dose was excreted from the body over a period of 2 weeks with fecal excretion as the primary route of elimination. The drug is excreted mainly as polar conjugates, with unchanged drug and unconjugated metabolites accounting for less than 30% of the total fecal radioactivity.

#### Contraindications

Tamoxifen is contraindicated in patients with known hypersensitivity to the drug or any of its ingredients.

#### Drug-drug Interactions:

In vitro studies showed that erythromycin, cyclosporin, nifedipine, and diltiazem competitively inhibited formation of N-desmethyl tamoxifen with apparent K1 of 20, 1, 45 and 30 μM, respectively. The clinical significance of these in vitro studies is unknown.

#### Formulation, Appearance, Packaging, and Labeling

Tamoxifen is available in the following doses for oral administration:

- 10 mg Tablets. Each tablet contains 15.2 mg of tamoxifen citrate, which is equivalent to 10 mg of tamoxifen.
- 20 mg Tablets. Each tablet contains 30.4 mg of tamoxifen citrate, which is equivalent to 20 mg of tamoxifen.

The administered dose will be 20 mg daily.

#### Availability

Tamoxifen is commercially available. It is being obtained as commercial supply.

#### Storage and handling

Tamoxifen is commercially available. Patients will obtain tamoxifen from their local pharmacy.

#### Side Effects

Complete and updated adverse event information is available in the current IB and/or product package insert.

### **4.2 Accountability Records for Investigational Product(s)**

UCSF Investigational Drug Services (IDS) will manage drug accountability records for UCSF.

### **4.3 Ordering Investigational Product(s)**

UCSF will obtain pembrolizumab and vorinostat directly from Merck & Co., Inc. Tamoxifen is commercially available.

## **5 Treatment Plan**

### **5.1 Dosage and Administration**

All trial treatments will be administered on an outpatient basis.

Pembrolizumab 200 mg will be administered as a 30-minute IV infusion every 3 weeks. Treatment cycle intervals may be increased due to toxicity, as described in Section 5.2. Every effort should be made to target infusion timing to be as close to 30 minutes as possible. However, given the variability of infusion pumps, a window of -5 minutes and +10 minutes is permitted (i.e., infusion time is 30 minutes: -5 min/+10 min).

The Pharmacy Manual contains specific instructions for the preparation of the pembrolizumab infusion fluid and administration of infusion solution.

Selection of 200 mg as the appropriate dose for a switch to fixed dosing is based on simulation results indicating that 200 mg will provide exposures that are reasonably consistent with those obtained with 2 mg/kg dose and importantly will maintain individual patient exposures within the exposure range established in melanoma as associated with maximal clinical response. A population PK model, which characterized the influence of body weight and other patient covariates on exposure, has been developed using available data from 476 subjects from PN001. The distribution of exposures from the 200 mg fixed dose is predicted to considerably overlap those obtained with the 2 mg/kg dose, with some tendency for individual values to range slightly higher with the 200 mg fixed dose. The slight increase in PK variability predicted for the fixed-dose relative to weight-based dosing is not expected to be clinically important given that the range of individual exposures is well contained within the range of exposures shown in the melanoma studies of 2 and 10 mg/kg to provide similar efficacy and safety. The population PK evaluation revealed that there was no significant impact of tumor burden on exposure. In addition, exposure was similar between the NSCLC and melanoma indications. Therefore, there are no anticipated changes in exposure between different tumor types and indication settings. As vorinostat and tamoxifen are oral, self-administered drugs, drug diaries will be provided for assessing compliance with treatment. The diary will be provided each time vorinostat and tamoxifen are provided to the study participant to take home. Missed doses will be noted and will not be replaced. The participant will proceed with the next scheduled dose at the next scheduled time.

**Table 5.1 Trial Treatment**

Drug	Dose/ Potency	Dose Frequency	Route of Administration	Regimen/ Treatment Period	Use
Pembrolizumab	200 mg	Q3W	IV infusion	Day 1 of each 3 week cycle	Experimental

Trial treatment should begin on the day of randomization or as close as possible to the date on which treatment is allocated/assigned.

Trial treatment should be administered on Day 1 of each cycle after all procedures/assessments have been completed as detailed on the Trial Flow Chart (Section 6.0). Trial treatment may be administered up to 3 days before or after the scheduled Day 1 of each cycle due to administrative reasons.

**Table 5.2 Arm A Regimen Description**

Investigational Product	Premedication; precautions	Dose	Route	Schedule	Cycle Length
Pembrolizumab	No premedications No precautions	200 mg	Intravenous	Day 1, Week 1 Cycles 1+	3 weeks (21 days)
Vorinostat	Administer whole with food, if possible	400 mg	Oral	Days 4 of 7 days All cycles	
Tamoxifen	No premedications No precautions	20 mg (tablets)	Oral	Daily continuous All cycles	

**Table 5.3 Arm B Regimen Description**

Investigational Product	Premedication; precautions	Dose	Route	Schedule	Cycle Length
Pembrolizumab	No premedications No precautions	200 mg	Intravenous	Day 1, Week 1 Cycles 1+	3 weeks (21 days)
Tamoxifen	No premedications No precautions	20 mg (tablets)	Oral	Daily continuous All cycles	

Tamoxifen may be omitted in Arm B at the PI's discretion

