## 1.3 Rationale for the Proposed Study

### 1.3.1 Rationale

Immunotherapy responses have remained limited in ER+ breast cancer. Our preliminary and clinical data suggest that epigenetic priming may be a successful strategy to enhance immune response. However, epigenetic priming is predominantly successful in patients with tumors that have exhausted CD8 subpopulation.

This proposal is focused on the potential role of epigenetic immune priming to reverse therapy resistance in pre- and postmenopausal breast cancer. Initially focused on all hormone therapy

positive patients, data from our pilot study with epigenetic priming suggests that benefits are vastly different if the population is limited to those patients with a 20% or higher expression of CD8 cells with dual expression of PD-L1 and CTLA in tumors (or 10% in blood). The pilot study, therefore, has two objectives,

- a) to show that vorinostat can increase the efficacy of pembrolizumab in a select ER+ breast cancer patient population and
- b) a biomarker select patient population has a higher than expected response rate to pembrolizumab

The goal of immune priming is to increase the number and composition of tumor-infiltrating lymphocytes, which renders this a relevant approach to therapy resistant ER+ breast cancer. The goal of the biomarker selection is to enrich for a population who is immune responsive

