**1.3.1.3 Prior studies with vorinostat in breast cancer**

In a Phase II clinical trial, we evaluated the role of vorinostat (VOR) in reversing hormone therapy resistance in advanced breast cancer. In a single arm study, 43 patients (median age 56 years (31–71)) were treated. A total of 25 patients (58%) received prior adjuvant tamoxifen (TAM), 29 (67%) progressed on at least one prior chemotherapy regimen, 42 (98%) progressed after one, and 23 (54%) after two aromatase inhibitors. The objective response rate by RECIST

criteria was 19%, and the clinical benefit rate (response or stable disease  $\geq 24$  weeks) was 40%. The median response duration was 10.3 months (confidence interval: 8.1–12.4). Histone hyperacetylation and higher baseline HDAC2 levels correlated with response and responses were mainly seen in the 56% of patients who had a meaningful change in acetylation with vorinostat. Preclinical studies have further suggested that hormonal therapy must be continued even in the presence of an HDAC inhibitor.

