## 2.4 Exploratory (Correlative) Objectives

Exploratory Objective	Endpoint(s)
1. Evaluation of biomarker target threshold on response rate (retrospective cut off of 20% vs 10%)	Biomarker target threshold on response rate
2. To assess the ratio of effector T cells: regulatory T cells in blood and tumor biopsies pre- and post-therapy.	Ratio of effector T cells: regulatory T cells in blood and tumor biopsies pre- and post-therapy
3. To evaluate inflammatory T cell signature changes in blood and tumor biopsies pre- and post-therapy.	inflammatory T cell signature changes in blood and tumor biopsies pre- and post-therapy
4. To evaluate changes in number of myeloid-derived suppressor cells (MDSCs) in peripheral blood and tumor biopsies pre- and post-therapy.	changes in number of myeloid-derived suppressor cells (MDSCs) in peripheral blood and tumor biopsies pre- and post-therapy
5. To evaluate changes in histone acetylation in peripheral blood cells and tumor biopsies pre- and post-therapy	changes in histone acetylation in peripheral blood cells and tumor biopsies pre- and post-therapy
6. Initial comparison to vorinostat-induced PD-1 in lymphocytes, PD-L1 modulation	Comparison to vorinostat-induced PD-1 in lymphocytes, PD-L1 modulation
7. Nanostring and 10x sequencing and single cell immune phenotyping (on stored tissue for successful arms only)	Completion of Nanostring and 10x sequencing and single cell immune phenotyping (on stored tissue for successful arms only)
8. Impact of HDAC inhibition of response to pembrolizumab vs. pembrolizumab in biomarker enriched population	Impact of HDAC inhibition

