## 3 Study Design

### 3.1 Characteristics

We propose a single site Phase II, two-arm, open-label unblinded, 65-patient trial in patients with hormone therapy-resistant breast cancer (HTR) to test the role of epigenetic priming in a biomarker enriched patient population in HTR breast cancer. The two arms include Arm A: pembrolizumab, vorinostat, and tamoxifen and Arm B pembrolizumab and tamoxifen.

Patients will be evaluated for response at 9 weeks ( $\pm 1$  week) by RECIST1.1 (using IR-RECIST) and will continue on therapy if they have stable disease or response at the time of disease evaluations. Patients with progression on imaging but are clinically stable, may stay on study but will require follow-up staging after 4-6 weeks. Patients will be assessed continually for safety and tolerability as well as for any adverse events. If progression on therapy with pembrolizumab, patient may continue if clinically indicated and be re-evaluated after 4-8 weeks.

We will follow AEs of clinical interest as defined by Merck and will dose modify pembrolizumab as per Merck guidelines. We have significant prior experience with vorinostat, tamoxifen, and pembrolizumab combination and are facile with managing drug toxicities.

Tissue biopsies of all patients will be collected prior to enrollment to assess for pre-treatment of our immune signature and PD-L-1 expression. Follow up biopsies and peripheral blood collection will be taken from all patients post-treatment at 8-10 weeks to characterize changes in local tissue effects and antigen-specific cellular and humoral immune responses in peripheral blood.

Patients will be stratified by prior number of hormonal and chemotherapies.

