**No dose modification will be pursued for tamoxifen.**

**Hematologic Toxicity\***

**Adverse Event:\* Neutropenia**

While dose hold may apply for all days of occurrence, dose modification will only apply if neutropenia persists for day 1, 8, and 15 of each cycle. Dose modifications are not required if labs are drawn on other days and counts have recovered upon retreatment on days 1, 8, 15.

Neutropenia Febrile neutropenia	Management/Next Dose for Vorinostat
ANC $\geq$ 1000	100%
ANC: 500-1000	Hold for until $\leq$ grade 2 #, Restart at 75%: 300 mg qd for all subsequent cycles Second occurrence resume at 200 mg qd for all subsequent cycles Third occurrence: remove from study
ANC: 0-500	Hold for until $\leq$ grade 2 or less# Restart at 75%: 300 mg qd for all subsequent cycles Second occurrence resume at 200 mg qd for all subsequent cycles Third occurrence: discuss with sponsor and principal investigator, consider omitting alternate weeks

#Patient with a dose delay for more than 3 weeks in the first 2 cycles will need to be replaced for toxicity and efficacy assessments.

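### Table 5.3 allows tamoxifen to be omitted in Arm B only, with no criterion, so the Arm A versus Arm B contrast may not isolate vorinostat

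*Combined protocol and SAP*

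**What the plan says.** Section 3.1 sets out the arms as "Arm A: pembrolizumab, vorinostat, and tamoxifen and Arm B pembrolizumab and tamoxifen". The Abstract and sections 5.3 and 8.1.1 describe Arm B in the same way. Tables 5.2 and 5.3 both list tamoxifen 20 mg by mouth; the Arm A schedule reads "Daily continuous All cycles". Below Table 5.3, for Arm B alone, stands the sentence "Tamoxifen may be omitted in Arm B at the PI's discretion". Table 5.2 carries no such note.

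Elsewhere, section 5.2 states "No dose modification will be pursued for tamoxifen". The other routes off tamoxifen are the liver and eye rules in section 5.2, the immune-related restart rule in section 5.2.2 and general discontinuation in section 5.4. These follow from toxicity or general withdrawal and are not limited to one arm.

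One of the two objectives in section 1.3.1 is "to show that vorinostat can increase the efficacy of pembrolizumab in a select ER+ breast cancer patient population". Section 8.3.2 compares the arms on the proportion with stable disease or better at 24 weeks, and section 8.3.1 makes the efficacy analysis intention-to-treat. Neither mentions tamoxifen omission.

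**The concern.** A randomized contrast between pembrolizumab plus tamoxifen, with and without vorinostat, attributes a difference to vorinostat because everything else is meant to be the same. The Table 5.3 note lets a second drug differ, in one arm, by a decision taken with the assignment known and bound by no criterion.

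Two things are at stake. First, any disease control that tamoxifen provides would be missing from Arm B patients who do not receive it, and would appear in the contrast as benefit from vorinostat. The endpoint counts stable disease, so tamoxifen need not shrink tumours to matter. Second, Arm B's own two-stage test is powered in section 8.1.1 at a rate of 0.35 for pembrolizumab with tamoxifen; a patient without tamoxifen is not on that regimen.

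**Working it through.** **Inputs from section 8.1.1.** Arm A: 13 patients, stop at 2 or fewer responses, otherwise 35. Arm B: 11 patients, stop at 1 or fewer, otherwise 30, with success at 7 or more. Between-arm test: Fisher's exact test at 0.1, planned at 0.4 versus 0.1, stated power 72.53%. Sidedness is not stated.

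**Inputs that the documents do not give (assumptions).** The share f of Arm B omitting tamoxifen, and the contribution d of tamoxifen to the 24-week endpoint.

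**Method.** For each arm, the exact distribution of the final count s is:
- stopped at stage 1: P(s) = Bin(s; n1, p), for s at or below the stopping limit;
- continued: P(s) = Σ Bin(x; n1, p) × Bin(s − x; n2, p), summed over x above the limit.

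The chance of declaring A better is the sum of P_A × P_B over all pairs of outcomes with two-sided Fisher p ≤ 0.1 and the higher observed rate in A.

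**Check against the plan.** At 0.4 versus 0.1 this gives 72.44%, against 72.53% stated. The chance that A continues and B stops, for 46 patients in total, is 0.657, against about 65% stated. One-sided Fisher at 0.1 gives 79.7% and does not match, so the two-sided form is used.

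**Effect on the contrast if vorinostat does nothing.** Let r be the common rate on tamoxifen. Arm A responds at r and Arm B at r − f × d. The 5-point column is, for example, f = 0.5 and d = 0.10: 0.5 × 0.10 = 0.05.

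| Common rate r | No loss | 1 point | 5 points | 10 points |
|---|---|---|---|---|
| 0.10 (Arm B null; planning rate for B in the contrast) | 0.20% | 0.23% | 0.33% | 0.49% |
| 0.15 (Arm A null) | 1.23% | 1.40% | 2.23% | 3.55% |
| 0.20 | 2.71% | 3.11% | 5.18% | 8.86% |
| 0.30 | 4.74% | 5.48% | 9.37% | 16.64% |
| 0.35 (Arm B alternative) | 5.17% | 6.00% | 10.46% | 18.94% |
| 0.40 (Arm A alternative) | 5.03% | 5.89% | 10.56% | 19.69% |

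A two-sided 0.1 test allows about 5% in the A-better direction. A 5-point loss clearly exceeds that only at common rates of 0.30 or more.

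**Sensitivity to the test.** Section 8.3.2 names a Z-test adjusted for the two-stage design but does not give the adjustment. An unadjusted pooled Z-test, two-sided 0.1, moves from 0.5% to 0.8% at r = 0.10, 2.1% to 3.8% at 0.15 and 7.1% to 13.8% at 0.35 with a 5-point loss. The pattern is the same.

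**Effect on Arm B's own test.** Power is P(at least 2 of the first 11 and at least 7 of 30). The stage 1 stop is (1 − p)^11 + 11p(1 − p)^10.

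| Arm B rate | Power | Stage 1 futility stop |
|---|---|---|
| 0.35 (no loss) | 90.0% | 6.1% |
| 0.34 (1 point) | 88.3% | 6.9% |
| 0.30 (5 points) | 78.5% | 11.3% |

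**The case against.** The strongest reply is that the asymmetry may be deliberate. Section 1.3.1.3 reports: "Preclinical studies have further suggested that hormonal therapy must be continued even in the presence of an HDAC inhibitor". That is a reason to require tamoxifen with vorinostat but not without it. Exploratory objective 8 reads "Impact of HDAC inhibition of response to pembrolizumab vs. pembrolizumab in biomarker enriched population", and Arm B's null and alternative sentences in section 8.1.1 name pembrolizumab only. This is a fair account of how the clause could have arisen. But the plan does not give it as the reason, and it does not change what section 8.3.2 compares.

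Second, the documents point to a small tamoxifen effect. Section 1.1.3 says that patients with resistant disease gain little from endocrine treatment. The 10-20% second-line response in section 1.1.2 is specific neither to tamoxifen nor to this population. This stands, and it places the likely size near the low end of the tables. It does not bring it to zero, since section 3.3.1 does not require prior progression on tamoxifen. The high-rate rows, moreover, combine a good Arm B rate with no vorinostat effect, whereas section 2.1 expects Arm B to stop at stage 1. At a rate of 0.10, a 10-point tamoxifen effect would leave omitters with no responses at all, and the error rate still barely moves.

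Third, a reader might infer that the comparison is invalid, or that its error rate is doubled. The documents support neither. Intention-to-treat remains a valid comparison of two treatment policies, and the doubling at 0.35 depends on assumed values of f and d.

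Fourth, a reader might infer that the sentence is redundant and can simply be deleted, because section 3.3.2 already excludes "Known allergic reaction or intolerability to tamoxifen". That criterion covers only what is known at entry. Section 1.2.3 names thromboembolism as tamoxifen's most serious side effect, patients with earlier DVT may enrol on anticoagulation, and no other rule expressly allows tamoxifen alone to be stopped for such an event. Plain deletion could remove Arm B's only express route.

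**Conclusion.** The point holds as a possible, probably modest distortion. It is certain that the plan permits criterion-free omission in Arm B only, with the arm known, although both arms are defined as containing tamoxifen. It is not known whether the option will be used, or whether tamoxifen matters here. If both are so, the bias runs one way: towards Arm A in the contrast and against Arm B in its own test. Across the assumptions shown the effect runs from negligible (a 1-point loss, or low response rates) to material (5 points or more at rates of 0.30 and above). If either condition fails, there is no distortion.

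The asymmetry concerns this discretionary permission only. Arm A patients can also come off tamoxifen, through the toxicity and discontinuation rules. The change is worth making because it is cheap.

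**What to change.** Replace the sentence under Table 5.3 with one rule stated for both arms: tamoxifen 20 mg daily is given in all cycles and may be omitted or stopped on its own only for a tamoxifen-related toxicity or a medical contraindication, for example thromboembolism, with the reason and date entered on the CRF. This keeps a safety route, extends it to Arm A, and agrees with sections 3.1 and 8.1.1.

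If the sponsor wants to keep the Arm B-only option, state the reason next to Table 5.3, report the number omitting tamoxifen by arm, and say in section 8.3.2 that the contrast compares treatment policies (vorinostat plus any tamoxifen difference), not vorinostat alone. The CRF entry is needed in this case too: the diaries in section 5.1 are handed out with the drug, so a patient never given tamoxifen may have none.

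Cost: less discretion for the PI in Arm B and one CRF entry. The sample size of 65 and the power inputs do not change.
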